1.6 Age, Gender and Ethnicity

Prostate cancer is a disease of adult men, with exceptionally few diagnosed at 35 years of age. We have chosen an age range of ≥ 35 to ≤ 85 years, which represents nearly all patients treated locally with radiotherapy for adenocarcinoma of the prostate. Therefore, women and children are not candidates for this protocol. Based on standard NIH definitions, we estimate that approximately 40% of patients will be White, 24% African American, 35% Hispanic and 1% other at the University of Miami.

2.0 OBJECTIVES

2.1 Primary Objectives

- The primary objective is to determine the effect of radiation boost to the imaging detected lesions on initial complete biochemical response.

2.2. Secondary Objectives

- To determine the impact of SRT boost to the MRI-identified lesion on toxicity, health-related quality of life (HRQOL), prostate cancer-specific anxiety, and prostate cancer-specific QOL.
- To evaluate biochemical and clinical failure, failure-free survival, and overall survival.
- To determine the distribution and degree of expression of tissue biomarkers by US-directed biopsies for patients who choose to undergo the optional biopsies.
- Compare PET and MRI detected lesions
- To determine the incidence and relationship of circulating DNA and tumor cells to tissue biomarkers and initial complete biochemical response.

3.0 PATIENT SELECTION

Up to 80 participants will be accrued for the entire study (Phase II and Phase III). The study is currently in Phase II which will accrue up to 40 participants. For a description of the Phase III component of the trial, please refer to protocol version 7.0, dated 10/14/2015.

3.1 Inclusion Criteria

Unless otherwise specified, the following are required at enrollment:

- A. Prostate cancer patients with a PSA after prostatectomy of at least 0.1 ng/mL and up to 4.0 ng/mL within 3 months prior to enrollment.
- B. Patients with or without palpable abnormalities on digital rectal exam (DRE) are eligible.
- C. Minimum of 3 months since prostatectomy to allow for return of urinary continence and healing.
- D. Imaging detectable lesion or lesions in prostate bed or regional LN. Each lesion should be at least 0.4 cc and a maximum of 6 cc and was obtained \leq 3 months prior to protocol entry or enrollment.
- E. No evidence of metastatic (distant) disease (pelvic nodes are allowed up to common iliac).
- F. Negative bone scan if deemed necessary by treating physician obtained \leq 4 months prior to protocol entry or enrollment..
- G. No previous pelvic radiotherapy.
- H. Serum total testosterone taken within 3 months prior to enrollment.
- I. No concurrent, active malignancy, other than nonmetastatic skin cancer or early stage chronic lymphocytic leukemia (well-differentiated small cell lymphocytic lymphoma). If a prior malignancy is in remission for \geq 3 years then the patient is eligible.
- J. Ability to understand and the willingness to sign a written informed consent document.
- K. Zubrod performance status <2.
- L. Patients must agree to fill out quality of life/psychosocial questionnaires.

M. Age ≥ 35 and ≤ 85 years.

3.2 Exclusion Criteria

Unless otherwise specified, the following are required at enrollment:

- A. Prior androgen deprivation therapy is not permitted if it was within 6 months previous to signing consent form. (NOTE: Therapy given as part of the planned course of radiation is allowed)

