APPENDIX II. NATIONAL CANCER INSTITUTE (NCI) COMMON TOXICITY CRITERIA (CTC)	38
APPENDIX III. DATA AND SAFETY MONITORING PLAN	39
APPENDIX IV. ADDITIONAL ITEMS	40
APPENDIX V PERFORMANCE SCALES	41

SCHEMA:**Figure 1: Prospective trial schema**

PSA = Prostate-Specific Antigen; RT = Radiation Therapy; MRI= Magnetic resonance Imaging; SVI = Seminal Vesicles Invasion; SRT = Salvage Radiation Therapy; CTV = Clinical Target Volume; GTV = Gross Tumor Volume as defined by MRI; MT = Mapped Tumor, AD = Androgen Deprivation.

Randomization applicable as

*is not
of version 8.0 of the protocol.*

1. Randomization**A. Arm I: Standard Salvage Radiation Treatment (SSRT)**

A total dose of 68 Gy will be delivered in 34 fractions to the Clinical Target Volume (CTV), 51 Gy in 34 fractions can be given to the pelvic nodes. (Closed as of protocol version 8.0)

B. Arm II: MRI Targeted Boost SRT (MTSRT)

Dose escalation to the Dynamic Contrast Enhanced MRI (DCE-MRI)-defined dominant region(s) by dose painting at 2.25 Gy per fraction, while the rest of the Clinical Target Volume (CTV) receives 2.0 Gy a fraction to 68 Gy. The mapped tumor (MT) boost region will receive an absolute dose of 76.5 Gy. Assuming an α/β ratio of 3.0, this would be equivalent to 80 Gy in 2.0 Gy fractions.

2. Stratification (no longer required as of protocol version 8.0)**A. PSA (≤ 1 vs. > 1 ng/mL)****B. SVI or Positive Margins (Y = one or both vs. N =neither)****C. Androgen Deprivation (Y vs. N)****3. Eligibility Screening: Includes Dynamic Contrast Enhanced (DCE)-MRI/PET of prostate bed and pelvis****A. PSA of at least 0.1 and up to 4.0 ng/mL within 3 months prior to enrollment.****B. Patients with or without palpable abnormalities on digital rectal exam (DRE) are eligible.****C. Minimum of 3 months since prostatectomy to allow for return of urinary continence and healing.**

- D. Identifiable tumor lesion or lesions. The enhancing lesion in the prostate bed or regional LN should be at least 0.4 cc and a maximum of 6 cc and was obtained \leq 3 months prior to protocol entry or enrollment.
- E. No evidence of metastatic (distant) disease (pelvic nodes are allowed up to common iliac).
- F. Negative bone scan if deemed necessary by treating physician obtained \leq 4 months prior to protocol entry or enrollment.
- G. No previous pelvic radiotherapy.
- H. Serum total testosterone taken within 3 months prior to enrollment.

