5.4 Post-treatment Evaluations

- History and physical, performance status (Zubrod), and toxicity at 6 weeks, 3 months, and then every 6 months for 5.25 years after completion of RT.
- Blood (up to 5 tubes) work in relation to RT:
 - PSA at 6 weeks, 3 months, and then every 6 months for 5.25 years.
 - Serum total testosterone 9 months after completion of RT.
 - Blood for research fluid tests will be collected at 3 months, 9 months and 2-2.5 years after completion of RT.
- DCE-MRI and or PET with timed contrast at 3 months, 9 months, and 2-2.5 years after completion of RT.
 - Should a lesion be identified, the treating physician will discuss management decisions with the participant
- Bone scan for a PSA of ≥ 2 or physician concern for metastasis.
- Psychosocial questionnaires will be administered at follow-up at 6 weeks, 3 months, 9 months, 15 months and yearly to 5.25 years:
 - Memorial Anxiety Scale for Prostate Cancer patients (MAX-PC).
 - The Expanded Prostate Cancer Index Composite Questionnaire-SF-12 (EPIC-SF12).

- International Prostate Symptom Scale (IPSS) will be done at each follow-up visit for 5.25 years. This includes 6 weeks, 3 months and every 6 months after RT for 5.25 years.

Note: Measurements and follow-up visits should occur within \pm 2 weeks up to the 3 months visit and within \pm 8 weeks for subsequent measurements/visits

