9.1 Definitions

- *PSA response rate*: The proportion of study patients with PSA <0.1 ng/mL at 21 months after completion of study treatment.
- *Acute toxicity*: Toxicity occurring during treatment and within three months of completing treatment.
- *Late toxicity*: Toxicity occurring more than three months after treatment completion. *Failure rate*: The cumulative incidence of biochemical or clinical failure allowing for competing risk as needed. Clinical failure is defined as at least a 25% increase in the size of the tumor relative to the smallest volume recorded, or new extension of tumor beyond the capsule, or re-extension of tumor beyond the capsule after initial regression, or urinary obstructive symptoms with carcinoma found at TURP. Biochemical failure is defined as PSA \geq nadir + 2 ng/mL.

- *Failure-free Survival (FFS)*: The elapsed time from start of radiotherapy to first documented evidence of biochemical or clinical failure or death from any cause, whichever occurs first. In the absence of any event defining failure, follow-up time will be censored at the date of last documented failure-free status.
- *Overall Survival (OS)*: The elapsed time from start of radiotherapy to death from any cause. For surviving patients, follow-up will be censored at the date of last contact.
- *Biomarker expression*: Quantification of the amount of the biomarker specific immunohistochemical staining in the area of tumor.
- *QOL*: Two contemporary instruments will be utilized to assess patient function and bother (Expanded Prostate Cancer Index Composite-SF12 (EPIC-SF12) and prostate cancer-specific anxiety Memorial Anxiety Scale for Prostate Cancer patients (MAX-PC).

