14.1 Overview

This is a single-arm Phase II trial with the primary objective of determining whether MRI-targeted boost SRT (MTSRT) improves the rate of PSA response (i.e., PSA < 0.1 21 months post treatment completion) in men receiving radiation therapy due to rising PSA post-prostatectomy. Secondary objectives include evaluation acute and late occurring toxicity, quality of life, biochemical and clinical failure, and survival. Additionally, blood and biopsy tissue samples from study patients will provide data for various biomarker studies described in the Bankhead Coley Team Science project "Integrated biomarkers for individualized prostate cancer therapy".

A single stage design without interim analysis of the primary endpoint is proposed for this trial because it would not be practical or desirable to suspend accrual to accommodate an interim assessment of PSA response, which requires nine months follow-up. Moreover, PSA response is not a perfect near term surrogate for long term benefit and thus not a definitive basis for an early conclusion regarding efficacy. The trial involves standard therapy with dose escalation, and an evaluation of PSA response based on accrual of 40 evaluable patients will provide information needed to design a subsequent trial evaluating long term outcome. Early stopping rules based on monitoring the toxicity of study treatment are provided in Section 14.6.

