Evaluable: Patients who are study eligible and receive an initial dose of *MTSRT* will be considered *evaluable for safety*, regardless of whether or not the full course of radiation treatment is completed according to protocol. To be *evaluable for efficacy*, study eligible patients must either (1) complete radiation treatment and the nine month post treatment PSA assessment or (2) initiate therapy but develop evidence of biochemical or clinical failure, or die from causes related to prostate cancer, within nine months of stopping or completing treatment. In the latter case (2), which is expected to be rare, patients will be included as non-responders in the evaluation of PSA response rate. The set of patients who are evaluable for efficacy comprise the main analysis set.

Exclusions: Any patient who is enrolled on study but does not receive an initial dose of radiation treatment will be excluded from all efficacy analyses. Any patient who initiates treatment and is later found to be ineligible for study (e.g., protocol violation) will be withdrawn from study but will be followed for toxicity and clinical outcome; the experience of such patients will be characterized separately from that of patients who are evaluable for efficacy. Reasons for exclusion of enrolled patients from analysis of safety or efficacy will be characterized.

Study endpoints are defined in **Section 9.1**.

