14.5 Analysis plan

The main analysis of study findings will be done for all patients who meet evaluable criteria as stated in Section 14.3. As noted above, analyses of some secondary endpoints, including acute toxicity, psychosocial parameters, tissue and blood product-related biomarker distribution on US-guided biopsies, and initial MRI findings may be reported before the efficacy endpoints, including the primary endpoint. These secondary endpoints will be analyzed after all planned patients have been accrued, completed treatment and have a minimal potential follow-up of 3 months from the end of RT. An initial analysis of clinical outcome (efficacy) is planned after all patients have been assessed for PSA levels at 9 months and a final analysis will be done at the completion of the planned 5 year follow-up of all study patients. Statistical tests will be two-sided with 5% significance level.

Statistical analysis will include descriptive statistics for patient demographics and baseline disease characteristics. Counts and percentages will be used to summarize the distribution of categorical variables while median, range, mean and standard deviation will be used for continuous variables. Baseline characteristics will include age, race/ethnicity, PSA, PSA doubling time, pT-category, pathologic Gleason score, and performance status. Biomarker measurements and proteomic/genomic profiles obtained from baseline biopsy will also be summarized with descriptive statistics.[51]

Treatment received will be summarized by the number and duration of treatment delays, and the rates of discontinuation or completion. Safety analysis will include a detailed tabulation of acute and late occurring toxicity by type and grade. Additionally, we will estimate the cumulative incidence (from start of treatment) of grade 2+ and 3+ genitourinary (GU) toxicity and of grade 2+ and 3+ gastrointestinal

(GI) toxicity. Death without the toxicity of interest will be treated as a competing risk, and toxicity rates will be reported.

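### Androgen deprivation given with the planned radiotherapy is permitted but not named in the single-arm analysis, so a PSA response rate above 60% could partly reflect it rather than the boost

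*Combined protocol and SAP*

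**What the plan says.** **Permission.** Section 3.2 excludes androgen deprivation within six months before consent, with the note "Therapy given as part of the planned course of radiation is allowed". No limit is set on the share of men, the agent or the duration. Footnote a of the study calendar (Appendix I) expects such use: it asks for pre-enrolment blood to be drawn before androgen deprivation, if possible.

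**Former handling.** Item 2 of the Schema lists "Androgen Deprivation (Y vs. N") among three stratification factors, under the heading "Stratification (no longer required as of protocol version 8.0"). Section 14.4 now reads as not applicable.

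**Current design and analysis.** Section 14.1: "This is a single-arm Phase II trial with the primary objective of determining whether MRI-targeted boost SRT (MTSRT) improves the rate of PSA response". Section 14.2 expects 60% with standard salvage radiotherapy and sizes for 80%. Section 9.1 defines the endpoint as "The proportion of study patients with PSA <0.1 ng/mL at 21 months after completion of study treatment", with no condition on testosterone or hormonal therapy. The evaluability rule in 14.3 does not mention either. In 14.5, "Baseline characteristics will include age, race/ethnicity, PSA, PSA doubling time, pT-category, pathologic Gleason score, and performance status"; the primary endpoint is a single proportion with an exact 95% interval. Logistic models for PSA response cover baseline factors, without naming androgen deprivation.

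**Testosterone.** It is measured before enrolment and once afterwards: "Serum total testosterone 9 months after completion of RT" (5.4, repeated in Appendix I).

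**The concern.** The endpoint is a PSA threshold, and androgen deprivation lowers PSA by itself. When the trial was randomised, stratification kept the two arms comparable on this factor. With one arm and a fixed benchmark, comparability rests entirely on whether 60% is the right no-boost rate for the men actually enrolled, including whatever share receives androgen deprivation. Nothing in the plan checks that.

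At stake is the primary conclusion. Section 14.1 says the PSA-response result will inform the design of a later trial, so an estimate that mixes the two effects would carry forward.

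There is a related gap. Table 14.5 counts the start of subsequent therapy as an event for failure rate and failure-free survival, but PSA response has no such rule. The non-responder rule in 14.3 covers only biochemical or clinical failure, or prostate-cancer death, within nine months. As written, a man who starts new hormonal therapy between 9 and 21 months and has PSA below 0.1 ng/mL at 21 months counts as a responder.

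**Working it through.** **Inputs from the documents.** n = 40 evaluable, null rate 0.60, alternative 0.80, one-sided 5%, stated power 83.9% (14.2); exact 95% interval (14.5, primary endpoint); two-sided 5% tests (14.5).

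**Inputs assumed.** m = number of the 40 men given androgen deprivation: 8, 12 or 20. q = their response rate with no boost effect: 0.70, 0.80 or 0.90. Men without it respond at 0.60, which takes the benchmark to be deprivation-free. The documents give none of these.

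**Step 1: reproduce the plan's figure.** With X ~ Bin(40, p), the smallest r with P(X ≥ r | 0.60) ≤ 0.05 is r = 30. P(X ≥ 30 | 0.60) = 0.0352 and P(X ≥ 30 | 0.80) = 0.8392. The stated 83.9% reproduces as an exact one-sample binomial test.

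**Step 2: the cut-off implied by the written analysis.** The exact lower 95% limit for x of 40 is the 2.5% quantile of Beta(x, 41 − x). For x = 30 it is 58.8%, below 60%. For x = 31 it is 61.5%, above 60%. The two-sided interval therefore needs 31 responders, and P(X ≥ 31 | 0.60) = 0.0156.

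**Step 3: no boost effect, mixed population.** Responders = A + B, with A ~ Bin(m, q) and B ~ Bin(40 − m, 0.60) independent. Expected overall rate = [mq + (40 − m) × 0.60] / 40. For m = 20, q = 0.90 this is (18 + 12)/40 = 75%. For m = 8, q = 0.70 it is (5.6 + 19.2)/40 = 62%.

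| Men on deprivation | q | P(≥30 of 40) | P(≥31 of 40) |
|---|---|---|---|
| 0 | – | 3.5% | 1.6% |
| 8 | 0.70 | 5.9% | 2.8% |
| 8 | 0.80 | 9.4% | 4.7% |
| 8 | 0.90 | 14.2% | 7.6% |
| 12 | 0.70 | 7.6% | 3.7% |
| 12 | 0.80 | 14.5% | 7.8% |
| 12 | 0.90 | 25.1% | 14.9% |
| 20 | 0.70 | 12.0% | 6.3% |
| 20 | 0.80 | 30.4% | 19.0% |
| 20 | 0.90 | 58.6% | 43.2% |

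**Step 4: timing of testosterone against the endpoint.** Sections 9.0, 9.1, 14.1 and 14.2 define PSA response at 21 months. Nine months also appears: 14.3 requires patients to "complete radiation treatment and the nine month post treatment PSA assessment"; 14.1, 14.2, 14.5 and 14.6 refer to nine-month follow-up or assessment; and section 8.0 ties the endpoint PSA to the 9-month blood draw. If the endpoint is at 9 months, the scheduled testosterone coincides with it. If it is at 21 months, the last scheduled testosterone precedes it by 21 − 9 = 12 months.

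**The case against.** **The plan is not silent.** It bars recent prior androgen deprivation, requires a baseline testosterone, measures it again at 9 months, follows men with six-monthly history and examination, requires documentation of treatment (15.4), and tracks the start of subsequent therapy. The baseline list need not be exhaustive, and the logistic models could include androgen deprivation. All of this stands: a reader might infer that nobody could ever reconstruct exposure, and the documents do not support that. But none of these provisions commits the analysis to use the information, and none touches the primary comparison.

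**The timing gap depends on an unresolved contradiction.** A reader might infer that the endpoint was moved to 21 months and the testosterone left behind. The text supplied shows both times in use and records no such move. This part is therefore conditional: it applies if 21 months stands and falls away if 9 months does. The missing analysis by androgen deprivation remains either way.

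**Physician discretion.** A reader might infer that androgen deprivation is given at the treating physician's discretion. The protocol says that of pelvic nodal radiotherapy and the bone scan, not of androgen deprivation; it simply gives no rule. The point does not need the inference.

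**The size is assumed.** This is the strongest objection and it stands. If the 60% comes from a population with a similar share of treated men, most of the inflation disappears. The result also depends on the cut-off, as the two right-hand columns show.

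**Conclusion.** The point holds as a gap in the analysis plan. Androgen deprivation is permitted with the study radiotherapy, was considered important enough to stratify on, and is now named nowhere in the endpoint, evaluability rule, listed baseline variables or primary analysis. A single-arm rate compared with a fixed 60% cannot separate its contribution from that of the boost.

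The probabilities in the table show sensitivity; they do not estimate this trial's error rate. They require a deprivation-free 60%, no boost effect, 8 to 20 of 40 men treated, and 70-90% response among them. Reading them as the actual false-positive risk would go beyond the documents. The point merits a change before the primary analysis because the remedy is cheap and the main claim depends on it.

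**What to change.** 1. Record androgen-deprivation use with start and stop dates, and add it to the baseline table in 14.5. Dates are needed because a testosterone value shows only current suppression, not a lasting contribution from earlier treatment.
2. Report PSA response with an exact 95% interval separately for men with and without androgen deprivation, beside the overall result.
3. State whether the 60% benchmark includes men given androgen deprivation, and justify it for the expected mix before any claim is made against it. Setting the no-deprivation estimate against 60% is sound only if the 60% is itself deprivation-free.
4. Reconcile the 9- and 21-month passages. If 21 months stands, add a testosterone assay at that PSA draw and keep the 9-month one, which gives the earlier view of recovery.
5. Prespecify a sensitivity analysis that does not count as responders men who are still suppressed, or have started new hormonal therapy, by the endpoint draw.

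**Cost.** Plan wording, one more table, two dates per treated man, and one extra assay at an existing visit. Subgroup intervals will be wide: by the same exact method, 24 of 32 gives 57-89% and 6 of 8 gives 35-97%. The split is descriptive. A 60% versus 80% test confined to men without androgen deprivation would have 69.8% power with 32 men and 41.1% with 20 (exact one-sided 5%).

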3.3 Enrollment Procedures

3.3.1 Enrollment

Patients can be enrolled only after eligibility criteria are met. The eligibility checklist must be completed prior to initiation of the registration process.

All eligibility requirements should be reviewed by the study coordinator and the eligibility checklist should be completed and signed by the local Principal Investigator or designated Sub-PI prior to the patient being enrolled into the study.

3.3.2 Cancellation Guidelines

If a patient does not receive protocol therapy, the patient may be withdrawn from the study. Patients who are enrolled on study but not treated will be excluded from all analyses.

3.3.3 Emergency Registration

N/A.

4.0 TREATMENT PLAN

4.1 Pre-Enrollment Imaging

T2, T1 non-contrast, T1 DCE and DWI MRI scans will be done routinely, when possible, in all patients being planned for external beam radiotherapy for prostate cancer. These sequences will be routinely obtained at 2.5 mm intervals to include the pelvis and prostatic bed. It is suggested that a diet designed to reduce bowel gas may be recommended the day before the MRI. The patient will be instructed not to void before the scan, to mimic bladder position during treatment. MRI exclusions include ferromagnetic metal in body/eye, pacemaker, defibrillator, other mechanical device, or extreme claustrophobia (medication with anti-anxiety agents, such as Ativan, may be used). Since the DCE-MRI scan involves the use of gadolinium, renal function will be assessed to ensure it is adequate.

PET imaging when obtained (flucicloving F 18, Choline, PSMA or other): Will be performed per imaging center.

